3. STUDY OBJECTIVES

3.1 Primary objective

Primary objective is the superiority of PRT of the experimental treatment schedule in terms of disease-free survival (DFS)* compared to the standard arm. We will perform a hierarchical test, starting with non-inferiority as the first primary analysis. If this is significant, then testing superiority as the second component of the main analysis will be performed.

If only non-inferiority but not superiority is confirmed, the cosmetic results (key secondary endpoint) need to be better in the preoperative radiotherapy arm for the study to be able to change clinical practice.

The investigated PRT-schedule consists of 5x 2.7 Gy per week to 40.5 Gy Standard-RT** prior to surgery. In case of planned breast-conserving surgery, a boost has to be administered in case of residual tumor after NACT. The boost can be administered percutaneously as simultaneous integrated boost (5x per week additional 0.5 Gy to 48 G) or after whole breast irradiation (3x 3.5 Gy to 10.5 Gy) or as an intraoperative boost. Intraoperative radiotherapy is administered with 10 Gy electrons of adequate energy.

**Standard RT is defined as radiotherapy of the breast +/- boost +/- lymph node regions.

*DFS is defined as the time in months between the breast cancer diagnosis and the disease recurrence (local or regional recurrence, contralateral breast cancer, distant metastases, second invasive cancer or death of any cause).

Table 1: Definition of disease-free survival

Event	DFS	Time from randomisation until
Locoregional recurrence	E	Date of locoregional recurrence
Lymph node recurrence	E	Date of lymph node recurrence (in the ipsilateral axillary, supra-/infraclavicular (including Rotter), and internal mammary chain lymph nodes)
Contralateral breast cancer	E	Date of contralateral breast cancer
Any distant metastatic disease	E	Date of distant metastases
Invasive non-breast cancer	E	Date of invasive non-breast cancer diagnosis
Treatment-related death	E	Date of death
Death of breast cancer	E	Date of death
Death of other cancer	E	Date of death
Non-cancer related death	E	Date of death
Death of unknown cause	E	Date of death
Under observation without event or lost to follow-up	C	Date last follow-up

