4.4 Standard of care arm

Patients randomized to the standard of care arm will receive surgery according to the national S3 and AGO-guidelines including targeted axillary dissection (TAD), sentinel lymph node biopsy (SLNB) +/- axilla dissection (AD).

3-6 weeks later, when wound healing is complete, the adjuvant radiotherapy to the whole breast/chestwall will be administered.

According to the S3/AGO guidelines postoperative radiotherapy of the breast/chest wall +/- regional lymph nodes (5x 2.7 Gy per week to 40.5 Gy) is recommended. If indicated according S3/AGO guidelines, a boost radiotherapy (optional intraoperative radiotherapy with electrons = IOERT) should be administered either as simultaneous integrated Boost or as sequential boost (see below).

After breast conserving surgery:

Whole breast radiotherapy with 5x2.7 Gy/week → 40.5 Gy in 3 weeks
+/- boost either as integrated boost (5x 3.2 Gy, total dose 48 Gy) or as sequential boost (3x 3.5 Gy to 10.5 Gy, total dose 51 Gy) or intraoperative boost with IOERT (electrons 1x10 Gy)
+/- + lymph node irradiation (5x2.7 Gy/week → 40.5 Gy in 3 weeks)

After mastectomy:

- chest wall irradiation: 5x2.7 Gy/week → 40.5 Gy in 3 weeks
+/- lymph node irradiation (5x2.7 Gy/week → 40.5 Gy in 3 weeks)

The standard of care arm presented here is a brief summary, which does not claim to be exhaustive. For a detailed summary of the radiotherapeutic treatment in this study, refer to Chapter 6

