6.2 Surgery

All kinds of breast surgery in accordance with the S3- and AGO-guidelines are allowed, such as breast-conserving surgery, mastectomy, skin-sparing mastectomy, nipple-sparing mastectomy, as well as combined with expander, immediate or delayed reconstruction with implants or autologous flaps. Sufficient safety margins must be set according to the S3- and AGO-guidelines. Lymph node assessment needs to follow a sentinel node concept. Axillary dissection needs to be carried out according to S3-and AGO guidelines in patients treated within the standard arm and according to this protocol for patients within the experimental arm.

Surgery in the experimental arm (preoperative radiotherapy) is not allowed to be performed before radiation-induced acute skin toxicity has vastly disappeared. Surgery is recommended 2.5-4, latest 6 weeks after completion of preoperative radiotherapy. The patient presents 2 weeks after the completion of radiation therapy for the evaluation of acute side effects. The radiation oncologist will authorize the patient for surgery.

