6.4.2 Whole Breast Radiotherapy (WBRT)

In the experimental arm, WBRT should preferably begin 2-4 weeks after the last application of NACT. In case of persistent toxicity that is regarded critical for radiotherapy, up to 6 weeks are allowed. Surgery should be performed after disappearance of the acute radiation induced erythema, preferably 3-6 weeks after completion of pre-operative radiotherapy. In the standard arm, post-operative WBRT should start 3-6 (up to 8) weeks after surgery.

6.4.3 Indication for breast/chest wall and regional lymph node irradiation:

Experimental arm (preoperative radiotherapy)

Preoperative radiotherapy Arm

- all patients receive whole breast radiotherapy (5x 2.7 Gy to 40.5 Gy +/- Boost RT)
- indication for regional lymph node radiotherapy depends on the initial findings before the start of the NACT +/ targeted therapy (5x 2.7 Gy to 40.5 Gy)

Lymph node region	indicated, if initially
Level I*- IV	cN+
Internal mammary chain LN**	cN+ and >=1 of the following factors

1) Central or medial tumor location

- 2) ER/PR negative tumor
- 3) cT3 tumor
- 4) cT4 tumor
- 5) cN2
- 6) inflammatory tumors
- 7) enlarged lymph nodes in the internal mammary chain

* Subtotal RT of Level I- II (see CTV definitions)

** No Internal mammary chain radiotherapy for left sided cancers treated with trastuzumab +/- pertuzumab and/or relevant cardiac comorbidity

Note: indications depend on the pretherapeutic findings irrespective of response to neoadjuvant systemic therapy

* Limited radiotherapy of Level I+II (see CTV definition)

** No IMC radiotherapy for left sided cancers treated in case of trastuzumab+/- pertuzumab or relevant cardiac comorbidity

Standard arm (postoperative radiotherapy):

The indication for whole breast / chest wall, for regional lymph nodes and boost radiotherapy should be administered according to the current recommendations of the AGO guideline.

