In axillary lymph node irradiation, the PTV should be limited below the level of the axillary vein at a distance of 0.5cm to prevent lymphedema, unless positive lymph nodes including a 0.5cm CTV margin, cross this virtual boundary. Positive lymph nodes should be contoured with a margin of 0.5 cm. If a lymph node including a safety margin extends outside the PTV this volume should be added to the CTV.

Patients with initially negative clinical lymph node (cN0) and neoadjuvant therapy-induced negative pathologic lymph node (ycN0) status on biopsy, but subsequently found to have histologically confirmed lymph node metastases at the time of surgery, who did not receive radiation to the axillary lymph node (ALN) region in the experimental arm are recommended for postoperative radiotherapy of the lymph node regions with field margin connection. It is important to note that cumulative toxicities should be considered in both treatment plans, and the cumulative dose limits of organs should be adhered to without accounting for potential recoveries (as significant recovery within such a short timeframe is unlikely). Efforts should be made to minimize anatomical shifts between the two planning CTs to minimize additional uncertainties. The patient should be adequately informed about the potential for increased cumulative toxicity. In these cases, it is advisable to involve the study leadership closely in the planning and implementation of the therapy.

Standard Arm (postoperative radiotherapy)

In case of breast conserving surgery:

CTVb_low = total breast (excluding 5 mm below the skin) including the initial tumor volume + 5mm [+ 2cm skin in case of inflammatory cancer]
(Anatomically adjusted)

GTVp = tumor bed of the primary tumor (best marked by clips)

CTVp_high = GTVp + 0.5cm (Indication according to AGO guidelines)
(Anatomically adjusted)

CTVn = Level 3-4 + IMC (Indication according to AGO guidelines). Level 1+2 in case of remaining macroscopic tumor and insufficient axillary surgery (see AGO guidelines)

In case of mastectomy:

CTVlow_chestwall (after mastectomy without reconstruction):

CTV definition regarding chest wall postmastectomy radiotherapy (standard arm only) in case of no reconstruction should follow the RTOG recommendations

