SAEs that have occurred from the initiation of radiotherapy and up to 3 months after radiotherapy should be reported to the GBG on the corresponding form. The GBG will inform the study chairmen. At regular intervals, the SAEs that have occurred will be discussed by the Safety Board of the study. In addition, the heads of study will consider preventive or corrective measures if necessary.

A patient that gets pregnant during study treatment will be withdrawn from the study and documented as drop-out. It is necessary to report to the study centre by sending in the case report. Local documents such as but not limited to hospitalization reports, autopsy reports, pathology report and lab sheets shall be provided in pseudonymized format when requested. Furthermore, the patient will be monitored during her pregnancy and after delivery. The constitutions of both mother and child need to be documented even if deemed normal and if no adverse events occurred.

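### SAE reporting opens at the start of radiotherapy in both arms, so with one external-beam course it covers the first weeks after breast surgery in the experimental arm but not in the standard arm

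*Protocol*

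**What the plan says.** The SAE rule is in protocol section 6.8: "SAEs that have occurred from the initiation of radiotherapy and up to 3 months after radiotherapy should be reported to the GBG". It has no arm-specific start and does not mention surgery, and no other section sets an SAE reporting period. The reports go to the GBG and on to the study chairmen, and then: "At regular intervals, the SAEs that have occurred will be discussed by the Safety Board of the study".

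The order of treatment differs by arm:

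- **Experimental arm.** Section 6.2: "Surgery is recommended 2.5-4, latest 6 weeks after completion of preoperative radiotherapy". Section 4.5 gives the same outer limits of 2.5 and 6 weeks.
- **Standard arm.** Section 6.4.2: "In the standard arm, post-operative WBRT should start 3-6 (up to 8) weeks after surgery". Table 3 gives 4 to 8 weeks. Section 4.4 adds a condition: "3-6 weeks later, when wound healing is complete, the adjuvant radiotherapy to the whole breast/chestwall will be administered".

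Two groups fit neither pattern. Section 9.2.2 places patients who had surgery but no radiotherapy in the safety set, with the postoperative radiotherapy group. In the experimental arm, a sentinel node biopsy may precede radiotherapy. The synopsis describes it as obligatory, section 2.1 as strongly advised, and Table 4 places it in the column for 1 to 14 days before radiotherapy.

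Ordinary AE recording follows a different rule. Section 6.8 starts it before local therapy, after neoadjuvant chemotherapy, and asks for grade III to V events to be entered within 2 weeks of discovery.

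**The concern.** The trial compares two sequences of the same two local treatments. A window tied to one of those treatments must therefore sit differently around the other in each arm. Here the affected period is the weeks just after breast surgery, and surgical morbidity after preoperative radiotherapy is the safety question that the protocol itself raises in sections 2.1.1 and 4.6.

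In the standard arm, radiotherapy waits for the wound to heal. A serious wound complication that resolves before radiotherapy starts produces no SAE report. The same complication in the experimental arm does. The board would see early surgical SAEs mostly from one arm, without a valid comparison rate from the other. The distortion runs against the experimental arm. Section 4.8 lets the Study Chairman stop the study for undue risk, so lopsided SAE reports are undesirable even though no formal SAE comparison is planned.

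**Working it through.** The plan gives no figure to reproduce, so the check is timeline arithmetic. Surgery means definitive breast surgery and is day 0. Three months is taken as 13 weeks, or 91 days. The patient has one external-beam course.

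**Experimental arm.** Postoperative time covered = 13 weeks minus the gap from the end of radiotherapy to surgery.

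- Gap 2.5 weeks: 13 − 2.5 = 10.5 weeks covered.
- Gap 3 weeks: 13 − 3 = 10 weeks covered.
- Gap 6 weeks: 13 − 6 = 7 weeks covered.
- Latest pre-surgery visit in Table 4, 6 weeks + 10 days = 52 days: 91 − 52 = 39 days covered.

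**Standard arm.** Postoperative time not covered = the gap from surgery to the start of radiotherapy.

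- Section 6.4.2: 3 to 8 weeks, or 21 to 56 days.
- Table 3: 4 to 8 weeks, or 28 to 56 days.

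**First 21 postoperative days (days 0 to 20).** The experimental window covers 21 of 21, since even the shortest case above leaves 39 days. The standard window covers 0 of 21, since it opens on day 21 at the earliest. This holds at every interval that the protocol permits.

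**Reports at equal risk.** Let p be a common risk of an SAE in those 21 days. Per 100 patients treated with one external-beam course, the expected number of patients with a reportable SAE is 100p in the experimental arm and 0 in the standard arm. No assumption on how the risk is spread over the days is needed.

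**Later weeks.** The standard window runs on to 3 + 3 + 13 = 19 weeks after surgery (15 fractions, start at 3 weeks) or to 8 + 3.6 + 13 = 24.6 weeks (18 fractions, start at 8 weeks). The experimental window closes at 10.5 weeks at the latest. Between those points only the standard arm is covered. Counting SAEs over the windows as written is therefore not like for like in either direction.

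**Groups outside this pattern.**

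- Surgery only: radiotherapy never starts, so no window opens.
- Sentinel node biopsy before radiotherapy, experimental arm: by Table 4 the window opens 1 to 14 days after the biopsy, and SAEs before that are outside it.
- Intraoperative boost, allowed in both arms: the protocol does not say whether it counts as initiation of radiotherapy. If it does, the standard-arm window opens at surgery for those patients. The protocol gives no figure for how many there will be.
- Postoperative nodal radiotherapy after preoperative radiotherapy: section 6.4.6 says that certain patients "in the experimental arm are recommended for postoperative radiotherapy of the lymph node regions with field margin connection". Their window then extends further after surgery.

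**The case against.** The strongest objection is that little information is lost. AEs are recorded from before local therapy in both arms, both schedules have a clinical assessment about 21 days after surgery, and grade III to V events are entered within 2 weeks. Deaths and life-threatening events are grades 5 and 4, so they should reach the database without an SAE form. The early reviews in sections 4.7 and 9.3.2 address wound healing directly from CTCAE-graded AEs. Section 6.8 says only that the board discusses SAEs and promises no comparison by arm. Much of this stands, and it limits the harm. It does not remove the point. Seriousness is not grade, so hospitalisations or lasting damage graded below III can be missed, and the SAE route to the GBG, the chairmen and the board stays lopsided.

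A second objection is that a radiotherapy anchor is a recognisable choice, because standard-arm surgery follows routine guidelines. A reader might take the mention of surgical treatment in the 6.8 heading, or the exemption for re-resection after an R1 finding, as proof that standard-arm surgery was meant to be covered. Neither proves it, since experimental-arm surgery falls inside the window and would need the same exemption. The point rests on the unequal coverage, not on presumed intent.

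A third objection is that the experimental arm is not fully covered either, because of the sentinel node biopsy before radiotherapy. That is correct, and the comparison above is confined to definitive breast surgery.

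**Conclusion.** The point holds for SAE reporting around definitive breast surgery in patients given one external-beam course. The first 21 postoperative days are covered in the experimental arm and uncovered in the standard arm at every permitted interval. The whole uncovered standard-arm stretch is 21 to 56 days, or 28 to 56 by Table 3. This assumes that 3 months is 13 weeks and that the protocol intervals are kept.

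A reader might infer that serious early events in the standard arm go unrecorded, that the wound-healing reviews cannot see them, or that the efficacy result is at risk. The protocol supports none of these. AE recording runs in both arms from before local therapy, the wound-healing reviews draw on those AEs, no between-arm SAE test is planned, and disease-free survival does not depend on SAE forms. It would also be too strong to say that all surgery in the experimental arm is covered.

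The point is worth correcting because a stated rule produces one-sided reports on the trial's main safety question and is cheap to change. Separately, the acute-toxicity period ends 3 months after radiotherapy in section 3.2 but 3 months after surgery in section 8.3. That is a minor wording mismatch to reconcile and adds no weight here.

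**What to change.** In section 6.8, use the same anchors in both arms:

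- **Open** SAE reporting at the first local procedure after neoadjuvant chemotherapy: axillary surgery (including a sentinel node biopsy before radiotherapy), breast surgery or radiotherapy, whichever is earliest.
- **Close** it 3 months after the later of definitive breast surgery and the end of radiotherapy. State that delayed reconstruction, which section 6.2 allows, does not count. Otherwise the window could stay open until 3 months after such an operation, whenever it takes place.
- **Display.** Where SAEs are shown by arm, count surgical SAEs over the same period after definitive breast surgery, for example 3 months.

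Every patient who has definitive breast surgery then has at least 13 weeks of SAE reporting after it: 19 to 24.6 weeks in the standard arm with external-beam treatment, 13 weeks with surgery only, and at least 13 weeks in the experimental arm. An intraoperative boost or postoperative nodal radiotherapy needs no separate rule.

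The cost is a short rewording of 6.8 and some additional perioperative SAE forms, mainly in the standard arm. No treatment, visit or sample size changes. The differing statements on the sentinel node biopsy (synopsis, section 2.1, Table 4) and on the start of standard-arm radiotherapy (sections 4.4 and 6.4.2, Table 3) should be reconciled by the sponsor. The proposed window works under any of them.

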7. QUALITY ASSURANCE

Only study sites with a distinct expertise in multimodality breast cancer therapy will be approved to treat patients within the NeoRad study. The study center will request the dose plans from the first 10 Patients of each study site by means of DICOM/FFP-Server and give feedback to the physicians/physicists retrospectively. To ensure optimal treatment coverage, regular training on treatment planning and typical inhomogeneities will be provided. Following completion of the planning, treatment plans are to be sent to the study chairmen. For research the dose plans from all study sites will be collected.

8. VISITS AND FOLLOW-UP DIAGNOSTICS

8.1 Visits

Study visits after WBRT begin in week 2 after completion of WBRT. Additionally, in the standard treatment arm a visit 3 months after surgery is performed and a visit 6 months after WBRT. In the experimental arm a visit 2 weeks after WBRT/110 days prior to surgery is performed followed by a visit 3 months after surgery and 6 months after surgery. Afterwards, the visits will be repeated annually until year 10. For the schedule of study procedures see table 3 and 4.

8.2 Gynaecologic examinations, Mammography/breast sonography

The above should be performed according to German S3 and AGO guidelines.

8.3 Toxicity assessment

Assessment of acute toxicity of WBRT according to CTC toxicity-scoring systems:

- Every week during RT.
- At every visit up to 3 months after surgery in both arms

Assessment of late toxicity according to LENT-SOMA scoring-systems at every further follow-up (i.e. once a year)

8.4 Cosmetic evaluation

Assessment of cosmetic outcome (objective and subjective) will be done according to a 5-point-scoring system (van Limbergen) **before WBRT** and after 1, 3, 5, 7 and 9 years. Breast retraction assessment (BRA) will be performed before WBRT and after 3, 7, and 9 years.

8.5 Study schedule

Overview in Table 3/4

Table 3: Schedule of study procedures in the standard of care arm

	after biopsy or latest before first response evaluation after the 1. cycle of NACT	prior to first response assessment	end of NACT	1-14 days before surgery	surgery	day 21 (+/-5)	1-2 weeks before start of WBRT (WBRT start: 4-8 weeks after surgery)	WBRT week 1, 2, 3	2 weeks after WBRT (+/3 days)	3 months after surgery (+/-1 month)	6 months after WBRT	every year (+/-2 months) until 9 years after WBRT or end of study
screening for study	x											
in-/exclusion criteria	x											
written consent	x	x										
registration	x											
randomization		x										
biopsy or surgery of primary breast cancer	histology reports (including FNB in case of susp. LN)				x							
sentinel node biopsy					x (or AD according to guidelines)							
breast/LN sonography	x		x	x					x	x	x (according to guidelines)	
Staging according to guidelines (CT chest/abdomen, bone scan)	x											
medical history documentation	x											
medication log	x											
response assessment according to guidelines			x									
mammography	x								x	x (according to guidelines)		
surgery report including pathology report?					x							
radiotherapy							x					
quality of life questionnaire				x								at year 1, 3,5,7,9
report of (planned) surgery technique	x				x							
clinical assessment	x		x	x	x	x	x	x	x	x	x	
cosmetic scoring				x								year 1,3,5,7,9
BRA				x								year 3,7,9

Table 4: Schedule of study procedures in the experimental arm

	after biopsy or latest before first response evaluation after the 1.cycle of NACT	prior to first response assessment	1-14 days before WBRT	WBRT wk. 1, 2, 3	2 weeks after WBRT (+/- 3 days)	4-6 weeks after WBRT (+/- 10 days) before surgery	surgery	day 21 after surgery (+/- 5 days)	3 months after surgery (+/-10 days)	6 months after surgery (+/- 1 month)	every year (+/-2 months) until 9 years after surgery or end of study
Screening for study	x										
In-/exclusion criteria	x										
written consent	x	x									
registration	x										
randomization		x									
biopsy or surgery of primary breast cancer	histology reports (including FNB in case of susp. LN)		re-biopsy								
sentinel node biopsy			x								
breast/LN sonography	x		x						x	x	x (according to guidelines)
Staging according to guidelines (CT chest/abdomen, bone scan)	x										
medical history documentation	x										
medication log	x										
response assessment according to guidelines			x								
mammography	x								x	x	x (according to guidelines)
Surgery report including pathology report?						x					
radiotherapy				x							
quality of life questionnaire			x						x	x	at year 1, 3,5,7,9
report of (planned) surgery technique	x						x				
clinical assessment	x		x	x	x	x	x	x	x	x	year 1,3,5,7,9
cosmetic scoring			x								year 3,7,9
BRA			x								

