3.2 Secondary objectives

Assessment and comparison between randomized arms of

- 1) time to local recurrence [in affected breast] (LR) as a first site of recurrence: recurrence in affected breast counts as an event; regional recurrence, distant recurrence, contralateral breast cancer, invasive non-breast cancer, death due to any cause are considered competing risks.
- 2) time to regional recurrence (RR) as a first site of recurrence: recurrence in the regional lymph nodes counts as an event, local recurrence, distant recurrence, contralateral breast cancer, invasive non-breast cancer, death due to any cause are considered competing risks.
- 3) distant disease-free survival (DDFS): distant recurrence, invasive non-breast cancer and death due to any cause are considered as events.
- overall survival (OS): death due to any cause is considered as an event.
- 5) breast cancer specific survival (BCSS): death due to breast cancer is considered as an event; in case of unknown death cause all effort will be made to determine the cause; if at the time of analysis there are still any deaths due to the unknown reason, they will be counted as tumor-related (worst case principle).

Time for all time-to-event endpoints will be computed starting from randomization after end of NACT.

- 6) pathological complete remission (pCR, defined as ypT0/is ypN0) rates.
- 7) cosmetic results (5 Point Scoring System, key secondary objective and subjective
- 8) breast retraction assessment=BRA)
- 9) quality of life (EORTC C30 and EORTC QLQ-BR23)
- 10) rate of arm lymph edema >°I of the irradiated side
- 11) plexopathy >°I of brachial plexus of the irradiated side

12) acute (up to 3 months after the end of radiotherapy) and late (after 3 months) toxicity (CTC 5.0, LENT-SOMA)

Definitions of outcome measures (clinical Trials.gov):

1. local recurrence rate [in affected breast] (LR) [Time Frame: 6 to 10 years]
Rate of cancer that has recurred at the same location as the primary cancer. This is a way to measure how well the new treatment is working.
2. locoregional recurrence rate (LRR) [Time Frame: 6 to 10 years]
Rate of new cancer at any locations (regional lymph nodes, chest wall/mastectomy site) on side which was previously affected by the primary cancer.
This is a way to measure how well the new treatment is working.
3. disease metastases free survival (DMFS) [Time Frame: 6 to 10 years]

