Time interval beginning after randomisation in which the patient survives, and the cancer has not metastasized.
This is a way to measure how well the new treatment is working.
4. overall survival (OS) [Time Frame: 6 to 10 years]
Length of time beginning after randomisation in the study that the patient survives.
This is a way to measure how well the new treatment is working.
5. disease specific survival (DSS) [Time Frame: 6 to 10 years]
Length of time from the beginning of the study after randomisation in a study arm that the patient survives the specific cancer.
This is a way to measure how well the new treatment is working.
6. pathological complete remission (pCR)
defined as ypT0/is ypN0) rates.

7. Assessment of cosmetic results by the physicians and the patient using a 5-point Scoring System* [Time Frame: 6 to 10 years]

A grading scale is provided for cosmetic results (5 Point Scoring System):

E0 Excellent aesthetic result: At first sight no visible therapy sequelae. Both breasts have a similar appearance

E1 Good: minimal changes in pigmentation, a visible scar, localized teleangiectasia.

E2 Moderate: marked sequelae with a clear deformation of the breast contour, nipple displacement, or marked skin changes, but yet "acceptable".

E3 Bad: severe retraction or fibrosis, severe teleangiectasia.

E4 Complications: skin necrosis

It will be analyzed as an ordinal scale and (key secondary objective) dichotomized as "Excellent/good vs moderate or worse".

Assesment of cosmetic results by the physicians using breast retraction assessment-Score (BRA Score) * [Time Frame: 6 to 10 years]

*The BRA Score measures breast symmetry of the treated breast in comparison to the untreated breast. The average in the general population is 1.2 cm. A higher BRA score is worse. A BRA score of 0 cm is optimal.

8. Measurement of the quality of life (QOL): functional scale [Time Frame: 6 to 10 years]

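### Quality of life is scheduled at 3 and 6 months in the experimental arm only, so the arms cannot be compared between the pre-local-therapy questionnaire and year 1

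*Protocol*

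**What the plan says.** Section 3.2 introduces its list of endpoints with "Assessment and comparison between randomized arms of", and item 9 of that list is "quality of life (EORTC C30 and EORTC QLQ-BR23"). The outcome definitions later in the same section give the window: "Measurement of the quality of life (QOL): functional scale [Time Frame: 6 to 10 years"], with the same window for the symptom scales.

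The only timing of the questionnaire is in the two schedule tables of section 8.5, in the row "quality of life questionnaire".

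- Table 3, standard arm: one mark under "1-14 days before surgery", then years 1, 3, 5, 7 and 9. The cells under "3 months after surgery (+/-1 month") and "6 months after WBRT" are empty.
- Table 4, experimental arm: marks 1-14 days before WBRT, 3 months after surgery and 6 months after surgery, then the same five years.

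Section 8.1 confirms that the standard-arm visits exist: "in the standard treatment arm a visit 3 months after surgery is performed and a visit 6 months after WBRT". Section 8.4 sets times for cosmesis and BRA only. Section 9.3.2 leaves the details of the quality-of-life analysis to the SAP.

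**The concern.** An endpoint meant for comparison between arms needs measurements in both arms at corresponding times. Here the experimental arm completes two early questionnaires and the standard arm none, although standard-arm patients attend at about those times. The early experimental-arm scores can be described but have no randomised reference.

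The gap covers a period in which the protocol itself sees a possible cost of the new sequence. Section 4.6 says that more postoperative complications, wound healing disorders in particular, cannot be excluded. Section 4.7 builds early safety reviews around them, and section 3.2 lists acute toxicity up to 3 months after radiotherapy as an endpoint. The patient-reported side of that early trade-off could not be compared. The SAP cannot repair this, because no analysis recovers questionnaires that were never scheduled.

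**Working it through.** The plan states no figure for this point, so the check sets the two rows side by side and then looks at the visit timing.

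**Step 1. The quality-of-life rows (section 8.5).**

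| Time point | Standard arm (Table 3) | Experimental arm (Table 4) |
|---|---|---|
| Before first local treatment | yes (before surgery) | yes (before WBRT) |
| 3-month visit | visit exists, no questionnaire | yes |
| 6-month visit | visit exists, no questionnaire | yes |
| Years 1, 3, 5, 7, 9 | yes | yes |

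**Step 2. Counts.**
- Standard arm: 1 + 5 = 6.
- Experimental arm: 3 + 5 = 8.
- Shared: 1 + 5 = 6, so every standard-arm time point has a counterpart.
- Without a counterpart: 8 − 6 = 2. With 913 patients per arm (section 9.4) this is at most 2 × 913 = 1826 questionnaires before attrition. The figure equals the total sample size only by coincidence.

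**Step 3. Could the difference come from how the tables were read?** In the text version both rows have their full number of cells (12 in Table 3, 11 in Table 4), and the yearly entry is in the last column of each. A sideways shift moves marks but does not turn three into one. The two extra marks in Table 4 do not appear to be borrowed from other rows, since mammography and clinical assessment keep their own marks in the same columns. Errors nearby are nevertheless visible. In Table 4 the years for cosmetic scoring and BRA are one row too high, as section 8.4 shows. In Table 3 the radiotherapy mark is in the column before WBRT. A full cell count does not prove that every mark survived.

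**Step 4. Would questionnaires at the existing visits line up?** Take 1 month = 52/12 = 4.33 weeks. Inputs are a WBRT start 4-8 weeks after surgery (Table 3), a WBRT duration of 3 weeks (section 4.4, no sequential boost), and surgery 2.5-6 weeks after radiotherapy (section 4.5). The protocol gives other ranges for these intervals elsewhere; these are used only for illustration.

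- Standard arm, end of WBRT: 4 + 3 = 7 to 8 + 3 = 11 weeks after surgery.
- Standard arm, 3-month visit: 13 ± 4.33 = 8.7 to 17.3 weeks after surgery. Relative to the end of WBRT this is 8.7 − 11 = −2.3 to 17.3 − 7 = +10.3 weeks, so it can fall during radiotherapy.
- Experimental arm, 3-month visit: 13 weeks ± 10 days (1.4 weeks) = 11.6 to 14.4 weeks after surgery. This is 11.6 + 2.5 = 14.1 to 14.4 + 6 = 20.4 weeks after the end of radiotherapy.
- 6-month visit, nominal: 26 weeks after WBRT in the standard arm, which is 26 + 7 = 33 to 26 + 11 = 37 weeks after surgery. In the experimental arm it is 26 weeks after surgery.

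The 6-month and yearly visits thus count from the last local treatment in each arm (WBRT in one, surgery in the other). They nominally match on that origin but not on time since surgery. The 3-month visits match on time since surgery but not on time since radiotherapy or the end of local therapy.

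**The case against.** The strongest objection is that the tables are unreliable exactly where the point rests. The mammography row also differs in number of marks (three in Table 3, four in Table 4), so a lost mark in Table 3 cannot be excluded. This stands. It lowers confidence to moderate and makes a check of the source tables the first action. It does not remove the point, since the rows as read are complete in cell count and no prose gives another schedule.

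A reader might infer that the trial cannot compare quality of life in the first year at all, or that it loses the period in which sequencing matters most. The documents support neither. Both arms have a questionnaire before local therapy and one at year 1 (± 2 months), so only the interval between them is lost. The stated time frame is 6 to 10 years, the expected benefits are fewer late complications and better cosmesis (section 2.1), and acute radiation toxicity is expected to be moderate in both arms. Within the stated window the schedules agree.

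A reader might also infer that the quality-of-life results will be biased. That would require an analysis that pools unmatched visits. Section 9.3.2 defers those details to the SAP, which is not at hand, so this is a possibility and not a finding. The 1826 counts questionnaires without a comparator; it measures neither bias nor lost power.

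Finally, adding questionnaires alone would not make the early time points fully comparable. Step 4 confirms this, and the fix has to deal with it.

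**Conclusion.** The point holds in limited form. As the tables read, the 3- and 6-month questionnaires exist in the experimental arm only, and no randomised quality-of-life comparison is possible between the pre-local-therapy questionnaire and year 1. Two of the experimental arm's seven post-baseline time points are affected; the five at years 1, 3, 5, 7 and 9 are not. Neither the primary endpoint nor the long-term quality-of-life comparison is touched.

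The conclusion assumes that the two rows are reproduced correctly and that no questionnaire schedule exists outside section 8.5. It is worth correcting because the endpoint is declared as a between-arm comparison, the standard-arm visits already take place, and missing questionnaires cannot be recovered later. Confidence is moderate.

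**What to change.** 1. Check the two quality-of-life rows against the source tables, and correct the misaligned neighbouring rows if they are misaligned there too.
2. If the difference is real, add QLQ-C30 and QLQ-BR23 to the standard-arm visits 3 months after surgery and 6 months after WBRT in Table 3. If early quality of life is not wanted, explain or remove the two experimental-arm assessments instead.
3. State a common time origin or visit-matching rule for quality of life, for example time from randomisation or from the end of local therapy. The latter already matches the nominal 6-month and yearly visits, but not the 3-month visit.
4. State, in the protocol or the SAP, that between-arm comparisons use time points scheduled in both arms.

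The cost is a table amendment and two extra questionnaire sessions per standard-arm patient, at most 2 × 913 = 1826, at visits that already take place. Alignment of the early time points relative to radiotherapy will remain imperfect, above all at 3 months, and should be acknowledged when results are read. Standard-arm patients who pass these visits before the amendment cannot contribute to the early comparison.
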